Clinical records: Smoking history, comorbidities (Charlson Comorbidity Index), nutritional status (MNA-SF), physical performance (SPPB), medication use, pulmonary function tests, COPD exacerbations in the past year, CAT score, mMRC score, and St. George's Respiratory Questionnaire (SGRQ).

Laboratory tests: Blood samples for CBC, CRP, cholesterol, albumin, HbA1c, IL-6, and TNF- α (ELISA).

Sample Size Calculation:

Using PASS 15.0 for repeated-measures ANOVA ($\alpha = 0.05$, power = 90%), with a COPD prevalence of 15% and a 2:1 ratio for sarcopenic obesity vs. non-sarcopenic groups, the study requires 200 participants (33 sarcopenic obese, 33 non-obese sarcopenic, 72 obese non-sarcopenic, and 72 non-obese non-sarcopenic).

Diagnostic Criteria:

Sarcopenia: Asian Working Group criteria: SMI (InBody S10) $<7.0 \text{ kg/m}^2$ (men) or $<5.7 \text{ kg/m}^2$ (women); grip strength $<28 \text{ kg}$ (men) or $<18 \text{ kg}$ (women); gait speed $<0.8 \text{ m/s}$. **Obesity:** BMI $\geq 28 \text{ kg/m}^2$ or waist circumference $\geq 85 \text{ cm}$ (men)/ $\geq 80 \text{ cm}$ (women); body fat $\geq 24.3\%$ (men) or $\geq 33.2\%$ (women).

sarcopenic Obesity: Coexistence of sarcopenia and obesity.

Assessments:

Physical Performance: Short Physical Performance Battery (SPPB: balance, gait speed, chair stands; score 0–12).

Nutritional Status: Mini Nutritional Assessment (MNA-SF; score 0–12).

Phase Angle: Measured via InBody S10 at six frequencies (1kHz–1000kHz) across five body segments, calculated using resistance (R) and reactance (Xc):

$\text{PHA} = \arctan((\text{Xc_right arm} + \text{Xc_trunk} + \text{Xc_right leg}) / (\text{R_right arm} + \text{R_trunk} + \text{R_right leg})) \times 180^\circ / \pi$.

Follow-up Endpoints:

Primary: Changes in pulmonary function, dyspnea scores, and body composition at 2 years.

Secondary: Acute exacerbations, hospitalizations, or death within 2 years. Follow-ups at 6, 12, and 24 months.

Grouping patients based on whether they have sarcopenic obesity, the differences in clinical data between the two groups were analyzed. Statistical analysis was performed using SPSS 24.0 statistical software.

Analysis of Demographic Characteristics and Clinical Data:

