The age and gender distribution of the patients were described. Based on whether the patients had sarcopenic obesity, they were divided into two groups. The differences in clinical data between the two groups, including age distribution, smoking status, obesity-related body fat, pulmonary function, whole-body and segmental phase angle, were analyzed. Continuous variables were expressed as mean \pm standard deviation, and categorical variables were expressed as percentages. Differences between groups were analyzed using Student's t-test for continuous variables and the chi-square test for categorical variables, depending on the data type.

Analysis of Factors Associated with COPD Complicated by Sarcopenic Obesity:

Univariate and multivariate analyses were conducted on data from COPD patients with sarcopenic obesity. Using clinical data variables, nutritional status, physical activity capacity, whole-body and segmental phase angle, logistic regression was applied to analyze the factors associated with sarcopenic obesity in COPD patients.

Analysis of the Prognostic Predictive Value of Sarcopenic Obesity in Obstructive Pulmonary Disease:

The differences in hospital stay length, acute exacerbation readmission rate, and mortality between COPD patients with sarcopenic obesity and those without sarcopenia at baseline were compared. Kaplan-Meier analysis was used for statistical analysis, and differences were expressed using the log-rank test.

COSAT study

INFORMED CONSENT FORM

This document provides you with information to help you decide whether to participate in this clinical research study. Please read it carefully. If you have any questions, please direct them to the researcher in charge of this study.

Your participation in this study is voluntary. This research has been reviewed and approved by the institutional ethics review committee of our research institution.

The background, objectives, research process, and other important information are as follows:

Research Purpose:

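### Student's t-test and mean ± SD are fixed for every continuous variable in a roughly 1:5 comparison: the error rate is wrong if group SDs differ, and power is lost on skewed markers

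*Combined protocol and SAP*

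**What the plan says.** Under Analysis of Demographic Characteristics and Clinical Data, patients are split in two: "Based on whether the patients had sarcopenic obesity, they were divided into two groups". One rule covers all continuous variables. The summary is fixed ("Continuous variables were expressed as mean" ± SD), and so is the test, Student's "t-test for continuous variables and the chi-square test for categorical variables, depending on the data type". The closing words of that sentence only separate continuous from categorical variables. The plan has no variance or normality check, unequal-variance test, transformation, rank test or median/IQR.

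Sample Size Calculation plans "33 sarcopenic obese, 33 non-obese sarcopenic, 72 obese non-sarcopenic, and 72 non-obese non-sarcopenic" within a stated total of 200.

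Laboratory tests lists "Blood samples for CBC, CRP, cholesterol, albumin, HbA1c, IL-6" and TNF-alpha. Research Objectives includes the role of inflammation and metabolic disorder in sarcopenic obesity. The variables named for the two-group comparison include body fat, pulmonary function and phase angle. The list is open-ended and names no laboratory marker.

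**The concern.** Student's t-test ordinarily means the equal-variance, pooled test. With groups of similar size it tolerates unequal SDs. At about 1:5 it does not, because the pooled SD is dominated by the large group while the standard error of the difference is dominated by the small one. If the small group is the more variable, false positives rise. If it is the less variable, real differences are hidden.

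Unequal SDs are plausible from the design. Sarcopenic obesity is defined by cut-offs on muscle, BMI or waist, and body fat, while the comparison group pools three different phenotypes. For body fat and phase angle a wider spread in the pooled group would not surprise, though the documents do not show it.

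The second issue is power. Inflammatory markers are often right-skewed (an assumption here), and comparing raw means of skewed data is inefficient.

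**Working it through.** **1. The plan's own figure.** 33 + 33 + 72 + 72 = 210, not 200. The sarcopenic-obese group is 33 either way; the rest is 200 − 33 = 167 or 210 − 33 = 177. The repeated-measures ANOVA calculation cannot be rebuilt, because no effect size, SD, within-patient correlation or dropout is given. The mismatch is a separate matter; both splits are used below.

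**2. Type I error of the pooled test under unequal SDs.** Let r be the SD of the small group divided by that of the large group, with the latter set to 1.

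- Variance the test assumes: P = [(n₁−1)r² + (n₂−1)]/(n₁+n₂−2) × (1/n₁ + 1/n₂)
- True variance of the difference: T = r²/n₁ + 1/n₂
- Large-sample two-sided error: 2 × [1 − Φ(1.96 × √(P/T))]

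Example, 33 vs 167, r = 1.5: P = (32 × 2.25 + 166)/198 × 0.03629 = 0.04362; T = 2.25/33 + 1/167 = 0.07417; √(P/T) = 0.767; effective cut-off 1.503; error 13.3%.

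Example, r = 0.67: P = 0.03306; T = 0.01959; √(P/T) = 1.299; effective cut-off 2.546; error 1.1%.

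| r | Formula, 33 vs 167 | Formula, 33 vs 177 | Simulation, 167 / 177 |
|---|---|---|---|
| 0.5 | 0.3% | 0.2% | 0.3% / 0.2% |
| 0.67 | 1.1% | 1.0% | 1.0% / 1.0% |
| 0.8 | 2.3% | 2.3% | 2.3% / 2.4% |
| 1.0 | 5.0% | 5.0% | 5.1% / 4.9% |
| 1.25 | 9.1% | 9.2% | 9.0% / 9.4% |
| 1.5 | 13.3% | 13.5% | 12.9% / 13.3% |
| 2.0 | 20.2% | 20.7% | 20.0% / 20.5% |

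The simulations used normal data and 20,000 replicates per setting. Welch's test stayed between 4.5% and 5.4% throughout.

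The conservative side costs power. At r = 0.67 and a true difference of 0.4 SD of the large group (33 vs 167), the difference is 0.4/√0.01959 = 2.86 standard errors. Against the effective cut-off of about 2.55, power is about 62%. Against Welch's cut-off of about 2.0 it is about 81%.

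**3. Skew without unequal SDs.** With identical log-normal distributions in both groups (log-SD 0.5 to 1.5), Student's test on raw values rejected in 4.7% to 5.5% of runs. Skew plus imbalance alone therefore keeps the level.

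**4. Power on skewed markers.** Log-normal data with equal log-SD, 33 vs 167, 20,000 replicates; the log-SD and fold differences are assumptions.

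| Log-SD | Small group | Student, raw | Welch, logs |
|---|---|---|---|
| 0.5 | 1.5-fold higher | 98.1% | 98.6% |
| 0.8 | 1.5-fold higher | 68% | 74% |
| 1.0 | 1.5-fold higher | 47% | 55% |
| 1.2 | 1.5-fold higher | 34% | 42% |
| 1.0 | 1.5-fold lower | 27% | 55% |

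The losses for a higher value are under 1 point at log-SD 0.5 and about 6 to 8 points at 0.8 to 1.2. Mann-Whitney comes within about 2 points of Welch on logs.

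**5. Welch on raw skewed values.** With identical log-normal distributions its type I error is about 7% to 9% at log-SD 0.8 to 1.2. It is not a remedy for the markers.

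**The case against.** *No SDs are given.* Correct. A ratio of 1.1 gives only 6.6%, so the 13% and 20-21% figures describe substantial heterogeneity that may not occur. A reader might infer that imbalance and skewed markers by themselves push p-values far from nominal; step 3 shows that they do not.

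*The markers may not be covered.* No laboratory marker is named in the comparison list, and laboratory tests sit apart from clinical records in the data-collection section. Applying the rule to them is an inference. It is reasonable, since the list is open-ended and no other direct group comparison is given for them.

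*Other analyses address the same questions.* A reader might infer that these t-tests are the only planned analysis of inflammation or phase angle. The documents do not support that. The logistic regression names whole-body and segmental phase angle, and its clinical data variables may include the markers. This does not cure the problem, however. The score test of a univariate logistic model with model-based variance is (x̄₁ − x̄₂)²/[s²(1/n₁ + 1/n₂)], with s² the total variance, so it pools in the same way.

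*The 1:5 split is uncertain.* The 33 is a planning count with no recruitment quota, and the same section mentions a 2:1 ratio that does not fit the listed groups. With the formula in step 2 and r = 1.5, the error is 13.3% at 33:167, 10.7% at 50:150 and 8.6% at 66:134. A literal 2:1 (133:67) gives 2.6%, which reverses the direction. The size depends on the split actually recruited; the weakness of the pooled test under imbalance does not.

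*Low consequence.* The primary endpoints are 2-year changes, the prognostic comparison uses Kaplan-Meier and log-rank, and no decision rule hangs on these t-tests. That limits the importance, but does not make the pooled test the better choice.

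**Conclusion.** The point holds in conditional form. The plan fixes a pooled-variance test for a comparison of about 33 against 167 to 177 patients, with no alternative. If the SDs differ, the real level runs from about 1% (ratio 0.67) to 20-21% (ratio 2.0); if they are equal it is near 5%, skewed or not. If the inflammatory markers fall under the rule and are roughly log-normal, power is lost to a degree that ranges from negligible to about 28 points (55% − 27%, for a 1.5-fold lower value at log-SD 1.0).

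The SD ratios, log-SDs and fold differences are assumptions. The split is the planned one, and two-sided testing at 5% is assumed. Because these are supporting comparisons, the change should be made, but the study's main results do not stand or fall on it.

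**What to change.** Replace the sentence on group comparisons with wording such as:

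> Continuous variables are compared with Welch's t-test. CRP, IL-6 and TNF-alpha, and any other variables listed before analysis as right-skewed, are log-transformed and compared with Welch's test on the log scale, reported as geometric means with their ratio and 95% CI. Where values are zero or below the detection limit, the Mann-Whitney test with median and IQR is used.

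The list of log-transformed variables should be fixed before the data are examined, so that the test is not chosen after seeing results. Mean ± SD remains suitable for the roughly symmetric variables. Welch's test should not be applied to raw skewed values.

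The cost is SAP wording only: no extra patients, data or visits. If SDs turn out equal, Welch gives up little: on the log scale in step 4 it had about 1 to 2 points less power than the pooled test. The one drawback is that log-scale results are read as ratios, not differences in original units.

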**Research on the Construction of a Prognostic Model for COPD
Complicated with Sarcopenic Obesity Based on Bioelectrical
Impedance Phase Angle Technology (COSAT)**

Research Protocol

Main researchers: [name], [name]

Clinical research department: Respiratory and Critical Care

Medicine Sponsor: [name]

Ethics Review No.:2025K200

Scheme Version No: 01

Plan Preparation date: July 15th, 2025

Research Objectives:

This study aims to explore the diagnosis, impact, and prognostic factors of COPD complicated with sarcopenic obesity using multi-segment bioelectrical impedance phase angle technology. It seeks to clarify the diagnostic value and efficacy of body composition analysis in specific populations, analyze the relationship between phase angle and COPD severity as well as quality of life, investigate its predictive role for adverse outcomes, and reveal the effects of inflammation and metabolic disorders in sarcopenic obesity. The goal is to provide a basis for early screening and precise intervention to improve patient prognosis.

Proposed Research Methods

Inclusion Criteria

- (1) Age over 65 years;**
- (2) Ability to complete physical activity assessments and pulmonary function tests;**
- (3) Complete medical records, willingness to adhere to follow-up arrangements, and provision of adverse event reports via telephone or outpatient visits, with signed informed consent;**
- (4) COPD diagnosis based on the American Thoracic Society (ATS)/European Respiratory Society (ERS) GOLD definition, with a post-bronchodilator FEV1/FVC ratio < 0.70, current or former smokers with a smoking history of ≥ 10 pack-years.**

Exclusion Criteria:

- (1) Severe cognitive impairment or hand deformities (e.g., rheumatoid arthritis) preventing body composition measurements;**
- (2) Incomplete clinical or follow-up data or unwillingness/inability to undergo regular follow-up;**
- (3) Severe systemic edema;**
- (4) Presence of cardiac pacemakers or significant metal implants that may interfere with measurements;**
- (5) Voluntary withdrawal for any reason, including loss to follow-up.**

Data Collection:

Demographic and clinical data: Gender, smoking status (never, former, current), age, height, weight, waist circumference, BMI, skeletal muscle index (SMI), body fat content,

visceral fat index, and segmental phase angles measured via bioelectrical impedance analysis.

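### The associated-factors regression is stated on patients who all have its outcome, and no planned analysis can deliver the prognostic model named in the title

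*Combined protocol and SAP*

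**What the plan says.** All references are to the combined protocol and SAP.

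**Associated factors.** The section Analysis of Factors Associated with COPD Complicated by Sarcopenic Obesity opens: "Univariate and multivariate analyses were conducted on data from COPD patients with sarcopenic obesity". The next sentence gives the predictors ("Using clinical data variables, nutritional status, physical activity capacity, whole-body and segmental phase angle") and the method: "logistic regression was applied to analyze the factors associated with sarcopenic obesity in COPD patients". No predictor list or count follows.

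**Grouping.** The preceding section, on demographic and clinical data, splits everyone by SO status: "Based on whether the patients had sarcopenic obesity, they were divided into two groups".

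**Numbers.** The Sample Size Calculation says "the study requires 200 participants" and gives the groups as "33 sarcopenic obese, 33 non-obese sarcopenic, 72 obese non-sarcopenic, and 72 non-obese non-sarcopenic".

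**Prognosis.** The title announces construction of a prognostic model for COPD with SO. Research Objectives begins: "This study aims to explore the diagnosis, impact, and prognostic factors of COPD complicated with sarcopenic obesity". The same paragraph asks whether phase angle predicts adverse outcomes. The section on the prognostic value of SO compares SO patients with those who had no sarcopenia at baseline on length of stay, readmission for exacerbation and mortality, by Kaplan-Meier and log-rank. No regression model for outcomes appears anywhere in the plan.

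**The concern.** There are two separate problems.

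First, a logistic regression for having SO needs patients with and without SO. The stated population contains only the former. Followed literally, the associated-factors objective returns nothing. If the analyst repairs this silently, the comparator is open: the plan uses everyone without SO in one section and only those without sarcopenia in another. That choice, and the choice among many candidate predictors, could then be made after the data are seen.

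Second, the study's headline product is a prognostic model, and phase angle is its central measurement. The planned prognostic analysis uses SO status alone, without adjustment, and does not involve phase angle. If the plan is followed, the study ends without the model in its title and without an answer on whether phase angle predicts outcomes.

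**Working it through.** **1. The plan's own sample size.** The listed groups sum to 33 + 33 + 72 + 72 = 210, not the stated 200. The calculation cannot be rerun: it names repeated-measures ANOVA but gives no effect size, standard deviation, within-patient correlation or dropout. The ratio is worded as "a 2:1 ratio for sarcopenic obesity vs. non-sarcopenic groups", while the listed numbers run the other way (72/33 = 2.18). Both totals are therefore carried below, with 33 taken as the planned SO count (33/200 = 16.5%; 33/210 = 15.7%). Neither regression considered here was the basis of the calculation.

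**2. The factor regression as written.** Let y = 1 if SO is present. In the stated population y = 1 for all 33 patients, so the log-likelihood is the sum of log p over those patients. It rises towards 0 as the intercept goes to infinity, whatever the covariates. No finite estimate or odds ratio exists. A trial fit with 33 simulated patients, two random covariates and a constant outcome gave perfect-separation warnings and stopped on a singular matrix.

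**3. The factor regression on all enrolled patients.**
- Non-cases: 200 − 33 = 167, or 210 − 33 = 177. A contrast now exists.
- If the comparator were only those without sarcopenia, as in the prognostic section, it would be 72 + 72 = 144 and the 33 non-obese sarcopenic patients would drop out.
- The limiting count is 33 cases in every version. At 10 cases per parameter, 33/10 = 3.3, so about 3 parameters; at 5 per parameter, 33/5 = 6.6, so about 6.
- The plan gives no predictor count. For an assumed 10 to 25 parameters, cases per parameter run from 33/10 = 3.3 down to 33/25 = 1.3. Whole-body plus five segmental phase angles, at a single frequency, already make 6.

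**4. Circular predictors.** Under Diagnostic Criteria, SO is built from skeletal muscle index, grip strength, gait speed, BMI, waist circumference and body fat. Under Assessments, gait speed is also a component of the SPPB. Body composition is among the clinical data collected, and physical capacity is named as a predictor family. Entering any of these would partly regress the definition on itself.

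**5. What the prognostic analysis covers.** SO against no sarcopenia is 33 against 144 as listed, 177 patients in all; the remaining 33 are not used. There are no covariates and no phase angle. A log-rank test on one grouping variable yields neither a multivariable model nor an estimate for phase angle.

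**6. What a whole-cohort model could carry.** The documents give no event rate. For assumed 2-year event proportions, with N = 200 and 10 events per parameter:

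| Assumed proportion | Events (200 × proportion) | Parameters |
|---|---|---|
| 10% | 20 | 2 |
| 30% | 60 | 6 |
| 50% | 100 | 10 |
| 60% | 120 | 12 |

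Within the 33 SO patients, the same 10% to 60% gives 3.3 to 19.8 events, so 0 to 1 parameter.

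**The case against.** The best defence of the factor analysis is that its first sentence is only loose drafting. The next sentence sets the target as SO among COPD patients, the previous section splits the whole cohort by SO, and a logistic regression for SO status implies both groups. An analyst would discover the problem on the first fit. Most of this stands: the whole cohort is the likely intent. It does not make the correction unnecessary. The regression population is never stated correctly, and two comparators are in use (177 or 144 patients on the listed sizes), so intent alone does not settle which patients enter.

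On prognosis, a reader might infer from the title and objectives that the model is to be built only in the 33 SO patients, and so has too few events to be built at all. The documents do not support that. They define no model and restrict none to those 33. The one prognostic analysis treats SO as the prognostic variable, with a comparator group. The objective on phase angle is not limited to SO patients. The shortage of events would follow only from that restriction; the whole cohort could support a modest model over the assumed range.

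Ten cases or events per parameter is a rule of thumb and not part of the plan. It serves here to show scale, not as a threshold.

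**Conclusion.** The point holds in two parts.

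The factor regression is stated on a population in which its outcome is constant. This follows from the text alone and needs no assumption. It is probably a drafting error, and it should be corrected. After correction the constraint is the 33 planned cases, which support about 3 parameters at 10 cases each against several unlisted families of predictors, some of which define the outcome.

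The plan contains no analysis that can produce the prognostic model in the title or show whether phase angle predicts outcomes. This too follows from the text. How large a model the cohort can carry is not known from the documents: 2 to 12 parameters rests on assumed event proportions of 10% to 60%, on 200 patients, on no loss to follow-up, and on the 10-per-parameter rule.

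The gap is that the prognostic model is unspecified, not that it is confined to a subgroup too small to support it.

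**What to change.** 1. **Associated factors.** State that the logistic regression uses all enrolled COPD patients, with SO present versus absent as outcome. Prespecify a few predictors, about 3 parameters, and choose in advance which phase-angle measure enters. Exclude the measures that define SO: skeletal muscle index, grip strength, gait speed (and so the SPPB), BMI, waist circumference and body fat.
2. **Prognosis.** Add one multivariable model of a named 2-year outcome in the whole cohort, with SO status and phase angle as predictors. List any further predictors in order of priority beforehand, and let the observed number of events decide how many enter, before any association with outcome is examined. State how the model's performance will be checked. Keep the Kaplan-Meier and log-rank comparison as a supporting, unadjusted analysis.
3. **The SO subgroup.** Report outcomes within the 33 SO patients descriptively, as event counts with confidence intervals.
4. **Numbers.** Reconcile the stated 200 with the listed 210, so that the denominators of both analyses are fixed.

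The cost is a rewritten analysis paragraph, one added model and a matching line in the objectives. The data are already to be collected and no further patients are needed. The downside is a narrower claim: a model for older COPD patients that includes SO status, not a prognostic model specific to patients with SO.

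### The logistic model for factors associated with sarcopenic obesity does not exclude the measurements that define it, and sets no candidate list for 33 planned cases

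*Combined protocol and SAP*

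**What the plan says.** The section *Analysis of Factors Associated with COPD Complicated by Sarcopenic Obesity* announces univariate and multivariate analyses and names the predictor domains: "Using clinical data variables, nutritional status, physical activity capacity, whole-body and segmental phase angle, logistic regression was applied". It gives no variable list, no exclusions, no maximum number of candidates, no rule for moving from the univariate to the multivariable step, and no penalisation.

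Under *Diagnostic Criteria* the outcome is "Coexistence of sarcopenia and obesity". Sarcopenia is judged on SMI, grip strength and gait speed; obesity is judged on BMI, waist circumference and percentage body fat. How the criteria combine is not fully stated.

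*Data Collection* places "waist circumference, BMI, skeletal muscle index (SMI), body fat content" under its demographic and clinical data heading. The two-group comparison that precedes the model uses the same vocabulary: "The differences in clinical data between the two groups, including age distribution, smoking status, obesity-related body fat". *Assessments* describes the physical performance measure as "Short Physical Performance Battery (SPPB: balance, gait speed, chair stands".

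*Sample Size Calculation* plans 33 participants with sarcopenic obesity. That calculation is for a repeated-measures ANOVA and does not address this model.

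**The concern.** A regression of a diagnosis on its own criteria is partly circular. If SMI or body fat is a predictor, a strong odds ratio is largely built in by the cut-offs and says little about what accompanies sarcopenic obesity in COPD. A reader could still take it for a discovered factor.

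The variable the study is built around, phase angle, could also be affected. It is not part of the definition, so its univariate association is sound in this respect. Adjusting it for SMI, however, conditions on a component of the outcome and can remove part of the association of interest.

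Separately, 33 cases support few parameters, and the plan leaves the number of candidates open.

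**Working it through.** **1. Case count.** The stated groups give 33 + 33 + 72 + 72 = 210, not the stated 200. That mismatch needs its own correction. The stated case count is 33 either way: 33/200 = 16.5%, 33/210 = 15.7%. Scaling the groups down to 200 would give 33 × 200/210 = 31.4 cases, which changes nothing below.

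**2. Definition set against predictor domains.**

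| Defining measurement | Route into the model |
|---|---|
| Body fat | Listed under *Data Collection*; also called clinical data in the two-group comparison |
| SMI, BMI, waist | Listed beside body fat under *Data Collection* |
| Gait speed | Through the SPPB, if that is what physical activity capacity means (inferred) |
| Grip strength | Not in the listed clinical data; no route found, but not excluded either |

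**3. Effect on the phase-angle coefficient (illustration only).** The documents give no correlations, so these are assumed: phase angle with SMI 0.3 to 0.7, with grip 0.3 or 0.5, with gait 0.3, with body fat −0.1; SMI with grip 0.4 and with gait 0.2; grip with gait 0.4. Prevalences follow the planned groups: sarcopenia (33 + 33)/210 = 66/210, obesity (33 + 72)/210 = one half. Sarcopenia is taken to require low SMI plus low grip and/or low gait speed.

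- Adding body fat alone changes the phase-angle coefficient by less than 15%.
- Adding SMI and body fat leaves between 5% and 71% of it. The 5% comes from a single combination (phase angle with SMI 0.7, with grip 0.3, low SMI and low grip both required); the next lowest value is 17%.

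The range is too wide to serve as an estimate. It shows that attenuation depends on SMI being entered, and that its size cannot be settled from the documents.

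**4. Events per candidate** = 33/p, counting each item as one parameter and phase angle at one frequency.

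| Reading | p | 33/p |
|---|---|---|
| MNA-SF, SPPB, whole-body and five segmental phase angles | 8 | 4.1 |
| Plus age, sex, smoking status, body fat, lung function | 13 | 2.5 |
| Plus height, weight, waist, BMI, SMI, visceral fat index | 19 | 1.7 |
| Plus the remaining clinical records and all laboratory items (CBC counted once) | 33 | 1.0 |

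Excluding defining variables does not solve this on the broadest reading: removing BMI, waist, SMI, body fat and SPPB leaves 33 − 5 = 28 candidates, and 33/28 = 1.2.

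**5. What few cases do.** Simulation assumptions: 33 cases of 200, three true predictors, the rest noise, all candidates entered together, 800 runs. Inflation is the mean estimate divided by the true coefficient, minus 1.

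| p | Mean estimate, true 0.5 | Mean estimate, true 0.8 | Inflation |
|---|---|---|---|
| 8 | 0.54 | 0.88 | 8% to 10% |
| 13 | 0.56 | 0.91 | 12% to 14% |
| 19 | 0.60 | 0.97 | 20% to 21% |
| 33 | 0.75 | 1.24 | 50% to 55% |

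A repeat with 400 runs gave 7% to 11% for p = 8 and 12% to 15% for p = 13. With independent null predictors tested at 0.05, the error rate per coefficient rises only to 5.1% (p = 8), 5.8% (p = 13) and 8.0% (p = 33).

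**6. What 33 cases can carry.** Ten events per parameter, a convention not found in the documents, gives 33/10 = 3.3. Five per parameter gives 33/5 = 6.6. A shrinkage criterion, p = n(S − 1)ln(1 − R²/S) with S = 0.9, n = 200 and R² on the Cox-Snell scale (maximum 0.592 at 16.5% cases), gives 2.1, 4.4 or 8.0 parameters for an assumed Nagelkerke R² of 0.15, 0.30 or 0.50.

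**7. Overlap among phase angles.** The formula in *Assessments* combines right arm, trunk and right leg but labels the result only PHA. If that is the whole-body value (inferred), it is built from the same resistance and reactance readings as three of the segmental angles, and entering them together makes the terms overlap.

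**The case against.** The strongest reply is that the model names four broad domains and no defining variable. Body fat is called clinical data in a different analysis, and SMI, BMI and waist come in only by carrying over a data-collection heading. Sensible analysts would leave them out. It stands that this is a missing exclusion and not a stated inclusion; a reader who inferred that the plan requires SMI or BMI as model terms would go beyond the text. But the plan's own vocabulary admits them, and nothing in it keeps them out.

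The overfitting figures assume that every candidate enters together, which the plan does not say. The inflation of about 50% therefore belongs to the broadest reading only and should not be quoted as the expected result. On the narrowest reading the inflation is modest and the false-positive rate per coefficient hardly moves. The aim here is association, not a deployed prediction rule.

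A reader might also infer that the model is to be fitted to cases only, because one sentence describes the data as those of COPD patients with the condition. Context resolves this: the same paragraph speaks of factors in COPD patients generally, and the preceding section splits patients into two groups. It is a wording slip.

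**Conclusion.** The point holds as a missing exclusion. Followed as written, the plan allows parts of the diagnosis to be reported as factors associated with it. This rests on the text for body fat, on the *Data Collection* heading for waist, BMI and SMI, and on an inference for gait speed.

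The documents do not support saying that the phase-angle findings are invalid. The univariate results are untouched, body fat alone changes the adjusted coefficient little, and attenuation requires SMI in the model, with a size that cannot be calculated from the plan.

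The candidate count is secondary: at most 4.1 events per candidate on any of the readings above if all are entered, with inflation of about 8% to 10% at that best case under the simulation's assumptions.

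This is a baseline association analysis and not one of the listed follow-up endpoints. It should be corrected before analysis, but it does not threaten the endpoints.

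**What to change.** Amend the section as follows:

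- State that the model is fitted on all enrolled COPD patients, with sarcopenic obesity yes/no as the outcome.
- Exclude SMI, grip strength, gait speed, BMI, waist circumference and body fat as predictors.
- Omit the SPPB, or replace it with its balance and chair-stand components. These are no longer the 0 to 12 score that the protocol defines and should be labelled accordingly.
- Prespecify a short candidate list that includes whole-body phase angle, sized to 33 cases: about 3 parameters under the assumed ten-events convention, roughly 2 to 8 under the other assumptions above. Alternatively, use penalised estimation.
- Do not enter whole-body and segmental phase angles in the same model, and state whether the PHA formula gives the whole-body value.
- Label the analysis exploratory.

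The cost is SAP wording, with no new data. Fewer factors can be reported, and the SPPB is lost or reduced as a predictor.
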